***In vitro* cough transportability**

A simulated cough machine is used to measure the airflow-dependent clearability of sputum. A model Plexiglas "trachea", rectangular in cross section (1.2 x 2 cm) is connected to an 8 L tank containing air pressurized to 8 psi giving a flow of about 11 L/s. A solenoid controls air release through a flow constrictive element used to mimic the airflow pattern of a natural cough. A sinusoidal constriction (length 7.7 cm and height 8 mm) is used to decrease the airway diameter while minimizing the turbulence (Reynolds number) of the system. A sample, 40 μ l in volume and 0.5 mm in depth, is placed in a thin line across the base of the Plexiglas trachea. The bulk transport of the sample is measured in mm after a single cough maneuver. Three successive measurements are made and the results averaged (3).

Mucus hydration (% solids), and mucus density

A mucus sample is weighed in a microbalance and dried for 4 hours in a lyophilizer. The dried sample is then reweighed in order to calculate the percent solids composition. The density of the mucus is also calculated by dividing the weight of the sample by the volume. As the density of mucus should be 1.00 ± 0.15 , this measurement is used as a check on the validity of the hydration measurement.

SLEEP DURATION ANALYSIS

Actigraphy provides a precise measurement of the motion of the part of the body to which a device is attached. Sleep/wake patterns will be recorded using the Actiwatch® 2. The data collected by the Actiwatch® 2 will provide objective and reliable data of the subject's sleep/wake patterns during the study period without influence. The unique Subject Identification Number assigned at Day 0 will be the only identifier linking the subject and the actigraphy data. The device is similar in size to a wrist watch and is well-suited for use with younger subjects or those sensitive to wrist-worn devices. The data collected will be downloaded into a software program "Actiware". This software will be located on the Coordinator's password protected computer. The data will then be scored and analyzed into predetermined intervals that will identify the epoch as either periods of wake or sleep. Statistics including Time in Bed (TIB), Total Sleep Time (TST), Wake After Sleep Onset (WASO), Sleep Efficiency (SE), Number of Wake Bouts (NWB) and Sleep Onset Latency (SOL) can be tracked over the study period.

Data Analysis

Statistical analysis of data will be performed using the JMP Pro 10 statistics package (SAS Institute, Cary, NC). Normality of data distribution will be visually checked and normally distributed data will be compared using two-tailed t-test and ANOVA. A $p < 0.05$ will be considered statistically significant. All results will be presented as means + the standard error of the mean.

QUALITATIVE EVALUATION

One sleep and three separate quality of life evaluations will be administered at various time-points according to Table 2 - Study Procedures. The information provided by the questionnaires will be transposed into the REDCap database by the study coordinator. All paper documents will be de-identified, the only identifier is the Subject Identification Number, which is kept in a locked cabinet, in the study coordinator's locked office.

Leeds Sleep Evaluation Questionnaire (LSEQ)

The Leeds Sleep Evaluation Questionnaire (LSEQ) is a 10-item, subjective, self-report, 5-10 minute paper and pencil measure designed to assess changes in sleep quality over the course of a psychopharmacological treatment intervention. The scale evaluates four domains: ease of initiating sleep, quality of sleep, ease of waking and behavior following wakefulness using paper and pencil. Developers initially validated the LSEQ in individuals aged 18-49 years. In the evaluation "initiating sleep" and the "quality of sleep" factors were correlated with one another while "awakening from sleep" and "behavior following wakefulness" factors were also correlated. Of the validated scales available to use for this study the LSEQ appears to be the most appropriate given the study being conducted.

Cystic Fibrosis Questionnaire-Revised (CFQ-R)

The Cystic Fibrosis Questionnaire-Revised (CFQ-R) is health-related quality of life (HRQoL) measure for children, adolescents and adults with CF. Initially it was developed through interviews with CF patients and healthcare providers and various focus groups and has since undergone comprehensive reliability and validity testing. This revised questionnaire is one of the most widely used HRQoL tests for CF. The CFQ-R measures how well an individual functions in a variety of domains, including Physical Functioning, Vitality, Health Perceptions, Respiratory Symptoms, Treatment Burden, Role Functioning, Emotional Functioning, and Social Functioning. This questionnaire is written for the intended age group in regards to language and length of questionnaire.

The Sino-Nasal Outcome Test (SNOT-20)

The Sino-Nasal Outcome Test 20 (SNOT-20) is a validated, health-related quality of life (HRQoL) questionnaire designed to determine the impact of nasal dysfunction on an individual's social/emotional health. This test consists of 20 questions and asks patients to assess nasal symptoms, emotion, and activity on a scale of worsening symptoms scored 1 through 7 to provide a quantifiable score capable of disease severity.^{1,2}

Non-validated device comfort survey (VAS score)

The non-validated device comfort survey used for this study will be conducted using a VAS score. The VAS (visual analog scale) will be used to measured characteristics, such as pain, that cannot be directly measured. The subject will be asked to point to a face depicting various levels of pain on a VAS that corresponds to the associated pain level when on HHNC and high-flow therapies.

ETHICS

Institutional Review Board

This protocol and any accompanying material to be provided to a potential subject (such as advertisements, information sheets, or descriptions of the study used to obtain informed consent) will be submitted to an IRB by the investigators and approval from the IRB must be obtained prior to starting the study. This approval will be documented in a letter to the investigator specifying the protocol number, protocol version, protocol date, documents reviewed, and the date on which the committee met and granted the approval.

Any amendments made to the protocol after receipt of IRB approval must also be submitted to the IRB for approval prior to implementation, if appropriate or the study must be paused and no further recruitment made until approval of the amendments has been granted. All related correspondence and IRB approved documents will be retained in a regulatory binder located in a locked cabinet in the study coordinator's locked office.

Code of Conduct

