- To evaluate the effectiveness of 20 LPM HHNC therapy (Optiflow™ cannula and AIRVOT™2 device) – experimental therapy versus 5 LPM HHNC therapy (Optiflow™ cannula and AIRVOT™2 device) – control therapy on physiological outcomes in hospitalized subjects with cystic fibrosis during an acute exacerbation.

Secondary Objectives

- To determine if the experimental therapy has an effect on Quality of Life as measured by the Cystic Fibrosis Questionnaire - Revised (CFQ-R) compared to control therapy
- To determine the effect of the experimental therapy on sleep duration using actigraphy (Actiwatch® 2) and subjective sleep quality measured by the Leeds Sleep Evaluation Questionnaire (LSEQ) compared to control therapy
- To determine the effect of the experimental therapy on Quality of Life in respect to nasal dysfunction as measured by the Sino-Nasal Outcome Test (SNOT-20) compared to control therapy
- To determine the effect of the experimental therapy on comfort and ease of use using the non-validated comfort survey (VAS score) compared to control therapy

Primary Endpoints

- Change in sputum volume, cough transportability and hydration (% solids)
- Change in FEV₁ % predicted from admission to end of study.

STUDY DESIGN

The study is a single-center, randomized pilot study to evaluate the clinical effectiveness 20 LPM HHNC (Optiflow™ cannula and AIRVOT™2 device) experimental therapy, versus 5 LPM HHNC (Optiflow™ cannula and AIRVOT™2 device) control therapy, on specified outcomes in hospitalized subjects with cystic fibrosis during acute exacerbation.

Potential subjects will be identified in clinic before admission to the Children's Hospital of Richmond at VCU (CHoR) or Virginia Commonwealth University Medical. If potential subjects are not identified in clinic, they will be introduced to and informed of the study by a member of the study team within 24 hours of hospital admission.

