- Has any contraindications to HHNC as listed below:
 - Maxillofacial trauma
 - Complete nasal obstruction
 - Presence of suspected base of skull fracture
- Any contraindication that applies to CPAP/ NIV therapy

STUDY PROCEDURES

The study requires clinical observations and overnight intervention therapy for/up to the first 5 nights of hospitalization. The study procedures to be performed on/by each subject enrolled in the study are outlined in Table 2.

Table 2
STUDY PROCEDURES

Time point	Procedure/Assessment
SCREENING (Day 0) (In CF Clinic or within 24 hours of hospital admission)	
Admission into the Children's Hospital of Richmond or MCV Hospital for adult subjects (hospital).Introduction to study and review the study procedures/study device with the study coordinator and/or study doctorVerification of inclusion/exclusion criteria and signing of Informed Consent Document.Assignment of the unique Subject Identification NumberReview of medical history and treatment recordsBaseline tests (as part of standard of care as medically indicated)Completion of the Leeds Sleep Evaluation Questionnaire (LSEQ) by subject.Completion of the CF-specific health related quality of life survey (Cystic Fibrosis Questionnaire – Revised (CFQ-R) by subject.Completion of the Sino-Nasal Outcome Test (SNOT-20) by subject.Sputum sample collection (if possible)Randomization to intervention - either: 'Control Therapy' (Low Flow, heated and humidified air delivered at 5 LPM via Optiflow™ cannula and AIRVO™2 device) or 'Experimental Therapy' (High-Flow, heated and humidified air delivered at 20 LPM via Optiflow™ cannula and AIRVO™2 device)

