BASELINE Day 1 (Approximately 9:00 AM)	
The device will be turned off (unless the subject has awakened earlier, in which case the subject can turn off the device when they wake).Sputum sample will be collected (where possible) or collection of previously produced sputum to research laboratory by study coordinator by 10:00 AM.Study coordinator will ensure that the nasal cannula is removed from the device and washed with warm water and mild dish washing detergent and rinsed thoroughly with clean water. The study coordinator will then place the nasal cannula in a clean zip locked bag taped to the device until required.Completion of the Leeds Sleep Evaluation Questionnaire (LSEQ)Completion of the device comfort survey (VAS Score).The study coordinator will collect the device log, and review the previous night's medical records (including any test results or medication dispensed).
TREATMENT PHASE Day 2 – 5 (PM)	
There will be no collection of produced sputum during this time.There will be no surveys completed during this time.The study coordinator and/or the study doctor will continue to review the subject's treatment and medication records.

Table 2
STUDY PROCEDURES

Time point	Procedure/Assessment
	
 Subjects will be allowed to go to sleep at whatever time they choose but must turn on the device before sleep onset and leave it on throughout the sleep period. The nursing staff will be instructed to ensure the subject continues to wear the device during the night. If for some reason the device comes off, or is turned off, the nurse will record the event and will attempt to correctly reposition without disturbing the subject or if this is not successful the subject will be awakened to ensure correct cannula placement. If the subject is discharged between Day 2 – Day 5, then the date of discharge will follow the 'Discharge' study procedure in place of the 'Treatment Phase' study procedure

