DISCHARGE Day 6 (AM)* (*or earlier if discharged prior to 5 days of treatment)	
 The device will be turned off (unless the subject has wakened earlier), in which case the subject can turn off the device when they wake. Sputum sample will be collected (where possible) or collection of previously produced sputum to research laboratory by study coordinator by 10:00 AM. Subject will remove Actiwatch® 2 and Study Coordinator will download Actiwatch® 2 data Completion of the Leeds Sleep Evaluation Questionnaire (LSEQ) by subject Completion of the CF-specific health related quality of life survey (Cystic Fibrosis Questionnaire – Revised (CFQ-R) by subject Completion of the Sino-Nasal Outcome Test (SNOT-20) by subject Completion of the device comfort survey (VAS Score) by subject. The study coordinator will collect the device log, and review the previous night's medical records (including any test results or medication dispensed). A follow-up appointment in the CF clinic will be scheduled according to the study doctor's recommendations (as part of standard care). The subject will be reminded to call the study coordinator or the study doctor if there are any new problems, questions or concerns once discharged from the hospital.
Clinical Follow-up Appointment	
 The study coordinator and/or the study doctor will review the medical history and treatment records. Baseline tests (as part of standard of care as medically indicated) Completion of the Leeds Sleep Evaluation Questionnaire (LSEQ) by subject Completion of the CF-specific health related quality of life survey (Cystic Fibrosis Questionnaire – Revised (CFQ-R) by subject Completion of the Sino-Nasal Outcome Test (SNOT-20) by subject Sputum sample collection (if possible). The sputum will be delivered to the research laboratory by the Study Coordinator Study compensation

DATA HANDLING AND RECORD KEEPING

Power Calculation

No studies have evaluated the effect of high-flow HHNC therapy to improve sinopulmonary symptoms in CF. Thus, the current study is designed as a pilot study that is likely to be underpowered to reach significance.

Electronic Database Capture

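### The arms are compared without a baseline covariate and reported only as mean and SEM; ANCOVA on the pre-device value, with an arm difference and 95% CI, would usually be more precise at little average cost

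*Combined protocol and SAP*

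**What the plan says.** The primary objective is a between-arm comparison at two flow rates: "experimental therapy versus 5 LPM HHNC therapy". Under Primary Endpoints the sputum outcomes are given as "Change in sputum volume, cough transportability and hydration (% solids", and FEV₁ as a change in percent "predicted from admission to end of study".

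The comparative analysis is a few sentences under Data Analysis: "Normality of data distribution will be visually checked and normally distributed data will be compared using two-tailed t-test and ANOVA", with significance at p < 0.05. The reporting commitment is "All results will be presented as means + the standard error of the mean". No covariate, between-arm difference or confidence interval appears anywhere in the document.

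Table 2 bears on which baseline could be used:
- The screening (Day 0) row, before device use, lists "Sputum sample collection (if possible" and the CFQ-R and SNOT-20.
- The row labelled BASELINE Day 1 opens with "The device will be turned off (unless the subject has awakened earlier", so that visit follows device use.
- The discharge row says "Sputum sample will be collected (where possible".

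The Power Calculation section describes a pilot that is probably underpowered. It gives no effect size, SD or correlation.

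**The concern.** A change score uses the baseline with a fixed coefficient of 1. ANCOVA estimates that coefficient from the data. When the true slope is well below 1, as it is when baseline and end values correlate only moderately and have similar SDs, subtraction adds noise that ANCOVA would remove.

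At 15 subjects per arm in a self-declared underpowered pilot, the useful product is the estimated arm difference and its uncertainty. The plan promises neither. A reader given the mean, SEM and n of the change scores can rebuild an unadjusted interval, but nobody can rebuild a baseline-adjusted one from those summaries. The SEM also has to be converted back to an SD before it can help plan a later trial.

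**Working it through.** **Inputs from the documents.** 30 subjects, 15 per arm; two-sided test at 0.05; endpoints expressed as changes. The sample size is not derived from anything, so there is no planned precision or power to reproduce.

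**Assumed inputs.** Correlation r between baseline and end value; ratio k of end SD to baseline SD; n complete pairs per arm (N = 2n). None is in the documents, so ranges are shown. The model is linear and normal. Pairs may be fewer than 15 because sputum is collected only when it can be produced.

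**Formulas**, with baseline SD = 1:
- Change-score variance is proportional to k² + 1 − 2rk.
- ANCOVA variance is proportional to k²(1 − r²) × [1 + 1/(N − 4)]. The bracket is the average price of chance baseline imbalance.

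**Variance ratio, ANCOVA ÷ change score** (below 1 favours ANCOVA):

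| Pairs per arm, SD ratio | r = 0.3 | 0.5 | 0.7 | 0.8 | 0.9 |
|---|---|---|---|---|---|
| 15, k = 1 | 0.675 | 0.779 | 0.883 | 0.935 | 0.987 |
| 15, k = 0.8 | 0.521 | 0.593 | 0.652 | 0.665 | 0.631 |
| 15, k = 1.25 | 0.815 | 0.927 | 1.018 | 1.038 | 0.987 |
| 10, k = 1 | 0.691 | 0.797 | 0.903 | 0.956 | 1.009 |
| 8, k = 1 | 0.704 | 0.813 | 0.921 | 0.975 | 1.029 |

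Example: n = 15, k = 1, r = 0.5 gives 0.75 × 27/26 ÷ 1 = 0.779.

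**As 95% CI width.** With n = 15 and k = 1, take the square root of the ratio and multiply by the t quantiles, 2.052 (27 df) ÷ 2.048 (28 df). The interval is narrower by 17.7%, 11.6%, 5.9%, 3.2% and 0.5% at the five values of r. At r = 0.5 the half-width falls from 0.748 to 0.661 SD, and power for an assumed 0.8 SD effect rises from 56% to 67%.

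**Where ANCOVA loses.** With k = 1 the variance break-even is r = 2(N − 4)/(N − 3) − 1, which is 0.926, 0.882 and 0.846 for 15, 10 and 8 pairs. With k = 1.25 and 15 pairs it loses for r of about 0.65 to 0.89.

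The ratio is largest when the slope rk = 1. Both leading terms then equal k² − 1, and the ratio is 1 + 1/(N − 4) = 1.038, 1.063 and 1.083. In CI width that is about 2.1%, 3.5% and 4.8%.

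**That maximum is an average.** In one trial the inflation is 1 + t²/(N − 2), where t is the baseline-imbalance statistic. At slope 1 with 15 pairs, about 31% of trials exceed 3.8%, and 5% exceed 2.048²/28 = 15%. With 8 pairs, about 30% exceed 8.3%, and 5% exceed 2.145²/14 = 33%.

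**Simulation check.** With 40,000 normal trials per setting, variance ratios fell within 0.015 of the formula, and type I error was 0.048 to 0.052 for both methods.

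**Complete pairs.** A Day 0 change score needs the same pair as ANCOVA, so nobody extra is lost against it. End values can still be wasted. Suppose k = 1, r = 0.5, and each arm has 15 end values but only 10 pairs. ANCOVA on pairs has variance (2/10) × 0.75 × 17/16 = 0.159; an unadjusted comparison of all end values has 2/15 = 0.133.

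**The case against.** The strongest reply is that a change-score t-test in a randomised pilot is legitimate, and that every figure above rests on correlations the documents do not supply. If r is about 0.9, as it might be for some endpoint over a short stay, the gain is nil. If variability grows by the end visit, ANCOVA can be slightly worse. The missing interval is partly recoverable: with equal SEMs of change and 15 per arm, the half-width is 2.048 × √2 = 2.90 times the SEM. The normal-theory results also may not carry over to skewed outcomes such as transport distance, especially with 8 to 10 pairs.

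All of this stands, and it limits the point to approximately normal endpoints and to efficiency. It does not remove the asymmetry: over the assumed range the possible gain is much larger than the average possible loss. Because r is unknown beforehand, the choice should be fixed in the plan rather than made after seeing the data.

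Two stronger readings are tempting, and neither is supported. A reader might infer that the planned comparison is biased or invalid; with complete pairs, randomisation makes the change-score comparison unbiased. A reader might also take 3.8% as a ceiling on what ANCOVA can cost; it is an average over randomisations at a fixed number of pairs.

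**Conclusion.** The point holds as one of precision and reporting. The plan uses baseline only by subtraction and commits to no between-arm difference or interval. With equal SDs and 15 pairs per arm, ANCOVA would narrow the 95% CI by roughly 18% at r = 0.3, falling to under 1% at r = 0.9. The worst average variance loss is 3.8%, 6.3% or 8.3% with 15, 10 or 8 pairs per arm, and an unluckily imbalanced trial can lose more. These sizes depend on an assumed linear normal model and on assumed r, SD ratio and pair counts, so the actual gain for any one endpoint is unknown. The case for reporting the arm difference, its interval and the SD does not depend on r.

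**What to change.** Rewrite the Data Analysis paragraph as follows.

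1. Name one end visit for every endpoint. The sputum endpoints have none, and the end-of-study point for FEV₁ is not tied to a Table 2 visit. Table 2 does not name spirometry, so state where the paired FEV₁ values come from.
2. For approximately normal endpoints with a pre-device value (cough transportability, % solids, FEV₁ % predicted, CFQ-R, SNOT-20, and sputum volume if it is measured), make the primary comparison an ANCOVA of the end value on randomised arm and the Day 0/admission value. Do not use the visit labelled BASELINE Day 1 as the covariate, because it follows device use.
3. If subjects with an end value lack a Day 0 value, also report an analysis of everyone with an end value, for example with the missing covariate imputed without using outcome or arm. This cannot rescue a missing end value.
4. Leave comfort VAS and actigraphy unadjusted, since Table 2 lists no pre-device value for them. Do the same for the LSEQ, which the protocol itself describes as assessing change.
5. For each normally distributed endpoint, report the between-arm difference with 95% CI, the per-arm SD in place of the SEM, and the number analysed.

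The cost is a paragraph of text, no new data, one residual degree of freedom (28 to 27 with 15 pairs per arm) and, on average, a loss of at most a few percent in CI width. Endpoints that are not normal need a method of their own, which this change does not supply.

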Assent from a subject will be obtained if they are aged 10 to 17 years along with informed consent from the eligible subject's parent or legal guardian. Informed consent will be obtained from subjects aged 18 years or older. All informed consent/assent discussions will take place in a private room and be documented according to the Pediatric Research Office's 'Informed Consent Process Cover Sheet'. Potential subjects and family members will be given as much time as necessary to determine if they would like to participate in the study. No study team member will be present during this period to minimize any possible coercion.

After informed consent is obtained the subject will be assigned a unique ‘Subject Identification Number.’ This number will consist of ‘VCUFP##’, where the first subject will be ‘VCUFP01’, the second ‘VCUFP02’, and so forth. This unique identifier will be used instead of the subject’s name, birth date, etc., to identify the subject for all study records and data.

After Subject Identification Number assignment is performed, randomization will occur. The study team will use the website www.randomization.com to randomize 30 study conditions (15 experimental and 15 control). The Study Coordinator will follow the randomization table chronologically as new subjects are consented.

This study is designed to accommodate 30 subjects (15 subjects per group) (Table 1). The study population will be determined from previously diagnosed CF patients who receive their CF care at CHoR and Virginia Commonwealth University. Subjects will be aged 10 years and older who are experiencing a CF exacerbation that requires hospital admission and therapy.

Table 1
STUDY DESIGN

Study Group	Assigned Intervention	Total Number of Subjects
Control Therapy	Low-Flow, 5 LPM (via Optiflow™ cannula) Heated (34°C), humidified air	15
Experimental Therapy	High-Flow, 20 LPM (via Optiflow™ cannula) Heated (34°C), humidified air	15

If a subject requests to withdraw from the study at any point, they are asked to inform the study doctor. Withdrawal from the study will not affect standard treatment the subject will receive for their CF exacerbation or ongoing treatment they may require. Upon withdrawal, the subject will forfeit any compensation for study participation.

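### The plan does not say how repeated values per subject enter its t-tests and ANOVA; without a subject effect, errors would be wrong in either direction

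*Combined protocol and SAP*

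**What the plan says.** The statistical text is one short paragraph under Data Analysis. It names the software and a visual check of normality, then says that "normally distributed data will be compared using two-tailed t-test and ANOVA". A p-value below 0.05 "will be considered statistically significant". On presentation: "All results will be presented as means + the standard error of the mean". It names no unit of analysis, subject effect, paired or repeated-measures form, or per-subject summary, and no other section supplies one.

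The same subjects are measured repeatedly:

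- Sputum (where it can be produced) and the LSEQ: up to four times, at Day 0, Day 1, Day 6 or discharge, and clinic follow-up (Table 2).
- CFQ-R and SNOT-20: three times, at Day 0, discharge and follow-up. The comfort VAS: twice, at Day 1 and discharge.
- Actigraphy: Sleep Duration Analysis lists sleep statistics that "can be tracked over the study period", with at most five treatment nights.

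Qualitative Evaluation says only that the questionnaires will be "administered at various time-points according to Table 2". Both primary endpoints are defined as changes. FEV1 runs from admission to the end of the study; the sputum measures have no visits named.

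**The concern.** The t-test and an ANOVA with no subject effect both assume independent observations. Values from one subject at several visits or nights are not independent. The plan leaves the analyst to decide whether to take one visit, form a change, average, or enter every row, and these choices do not have the same error rate.

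Two features make the gap matter. First, with two arms and one value per subject, a one-way ANOVA is the same test as the t-test (F = t²). Naming ANOVA as well suggests that time points may be a factor, which is where the subject effect is needed. Second, sputum is collected only when possible and discharge may come early, so subjects will contribute unequal numbers of values and the analyst will have to improvise.

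At stake are the p-values and SEMs for the LSEQ, CFQ-R, SNOT-20, comfort VAS and actigraphy, and for sputum if several visits are used.

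**Working it through.** The plan gives no power, standard deviation or correlation, so there is no figure of its own to reproduce.

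**Inputs.** From the documents: 15 subjects per arm (Study Design, Table 1), two-sided 0.05 (Data Analysis), and m = 2 to 5 values per subject (Table 2; five-night maximum under Study devices/equipment). Assumed: within-subject correlation ρ = 0.3, 0.5 or 0.8, equal between all pairs of values.

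**Arm effect with all rows treated as independent.** The design effect is DE = 1 + (m − 1)ρ. The naive standard error is 1/√DE of the true one. The actual type I error is about 2 × [1 − Φ(1.96/√DE)].

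Example, m = 4 and ρ = 0.5: DE = 1 + 3 × 0.5 = 2.5; SE ratio = 1/√2.5 = 0.632; 1.96 × 0.632 = 1.24; type I error about 0.215. The 30 × 4 = 120 rows carry the information of 120/2.5 = 48 independent values.

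**Simulation.** 20,000 null trials per setting. Each cell gives type I error at ρ = 0.3 / 0.5 / 0.8, nominal 0.05.

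| m | t-test, pooled rows | ANOVA without subject effect: arm | Same ANOVA: arm-by-time |
|---|---|---|---|
| 2 | 0.086 / 0.114 / 0.147 | 0.084 / 0.110 / 0.142 | 0.021 / 0.006 / 0.000 |
| 3 | 0.121 / 0.163 / 0.232 | 0.119 / 0.158 / 0.225 | 0.015 / 0.003 / 0.000 |
| 4 | 0.156 / 0.224 / 0.300 | 0.153 / 0.217 / 0.289 | 0.013 / 0.002 / 0.000 |
| 5 | 0.186 / 0.266 / 0.352 | 0.182 / 0.259 / 0.341 | 0.011 / 0.001 / 0.000 |

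**Why the last column goes the other way.** Time and arm-by-time contrasts are made within subjects, so their true error variance is (1 − ρ)σ². Without a subject effect the ANOVA divides by about σ². Its F is then centred near 1 − ρ = 0.7, 0.5 or 0.2 instead of 1, and the standard error of a change is too large by 1/√(1 − ρ) = 1.20, 1.41 or 2.24. The time test was not simulated, but it has the same error term.

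**One value per subject.** A two-sample t-test on subject means or on a change between two fixed visits gave type I error of 0.047 to 0.053 in every setting, which is nominal. FEV1 change is in this position already. Sputum change is not yet: with four collection times and no visits named, more than one change can be formed.

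**The case against.** A reader might infer that the plan commits to an ordinary ANOVA on all rows and so understates its errors. The documents do not support that. They say only ANOVA, which can include a repeated-measures form. Nowhere do they say rows will be pooled, and the one replicate rule they give points the other way: the three cough-machine readings are averaged to one value. The argument from F = t² is only suggestive, since a second factor of any kind would also justify naming ANOVA.

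Nor do the primary endpoints inherit the problem as they stand, since both are changes. It would also be wrong to say that the errors are always too small; for time and arm-by-time they would be too large. A mean with its SEM across subjects at one visit is correct; it goes wrong only if visits are pooled.

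The larger error rates also need unlikely choices. Four rows would mix the pre-treatment Day 0 value and the post-discharge value into one arm contrast. CFQ-R and SNOT-20 have only two values after treatment starts, so the two-row figures fit them better. Five nights is a maximum, and nightly recording is inferred.

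Finally, this is a pilot: "the current study is designed as a pilot study that is likely to be underpowered to reach significance". That lowers the stakes, but the plan still sets a significance threshold, and a method that loses power on arm-by-time serves a small trial badly.

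All of this stands as a limit on the point. None of it supplies the missing specification.

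**Conclusion.** The point holds as a gap in specification, not as a demonstrated error. The plan should say how repeated values enter its tests. FEV1 change is unaffected, and sputum change will be once its two visits are named. For the other repeated outcomes, leaving out the subject effect would give, for the arm effect on pooled rows, type I error of about 9–15% with two values per subject and 16–30% with four. Tests of time and arm-by-time would run at about 1% or less with four values, at a cost in power. These figures assume pooling, 15 complete subjects per arm and equal within-subject correlation of 0.3 to 0.8; the documents give no correlation. Missing sputum samples or early discharge would lower the number of rows and so the size of the effect. The text should be settled before analysis.

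**What to change.** For outcomes measured at several visits, replace the t-test/ANOVA sentence with the following:

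1. **Model.** A linear mixed model with arm, visit, arm-by-visit and a subject random effect, adjusted for the Day 0 value. The reported result is the arm contrast at Day 6/discharge. The comfort VAS has no Day 0 value and is analysed without that adjustment.
2. **Missing Day 0 sputum.** Keep these subjects by modelling Day 0 as an outcome with a common mean across arms, not as a covariate.
3. **Baseline.** State that baseline is Day 0. The Day 1 visit carries the label BASELINE in Table 2, but it opens with the device being turned off and so follows the first device night. Name Day 0 and Day 6/discharge as the two visits for sputum change.
4. **Actigraphy.** Average each subject's nights to one value per statistic, then compare arms by t-test.
5. **Presentation.** Base every SEM on subjects, never on rows.

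A change between two named visits, or a repeated-measures ANOVA, would also give valid errors. The mixed model is preferable because subjects with incomplete visits stay in. Adjusting for Day 0 is also more precise than a change score: with equal variances the variance ratio is (1 − ρ²)/[2(1 − ρ)] = (1 + ρ)/2, or 0.65, 0.75 and 0.90 at ρ = 0.3, 0.5 and 0.8.

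The cost is a few lines of text and slightly more analysis work, with no new data. The downside is that arm p-values will be less favourable than pooled rows would give.
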